BIOMEDICAL RESEARCH PROTOCOL

UNIVERSITY OF MISSOURI

Project Title: The Use of Intranasal Calcitonin to Improve Pain and Activity in Elderly Pelvic Ring Injuries

IRB Number: 2013172

Version Number: 2

Version Date: 09/13/2019

Principal Investigator: [name]

Funding Source: AOTNA Grant

I. Research Objectives/Background

1. Include primary, secondary, and exploratory objectives.

Primary Objective: To compare acute pain over a three-month period in geriatric patients with pelvic ring injuries who receive intranasal salmon calcitonin with those who do not receive intranasal salmon calcitonin

Secondary Objective: To compare function and activity over a three-month period in geriatric patients with pelvic ring injuries who are treated nonoperatively and receive intranasal salmon calcitonin with those who do not receive intranasal salmon calcitonin.

Exploratory objective: To compare radiographic healing in geriatric patients with pelvic ring injuries who receive intranasal salmon calcitonin with those who do not receive intranasal salmon calcitonin

2. Include background and rationale for initiating the study. Includes pre-clinical and clinical data, current experiences with procedures, drug, or device, and any other relevant information to justify the research.

It is anticipated that geriatric patients who sustain pelvic ring injuries and are treated nonoperatively will demonstrate decreased pain scores and improved subjective and objective function if they are started on intranasal salmon calcitonin within 5 days of injury compared to patients who do not receive intranasal salmon calcitonin. It is anticipated the decreased pain and improved activity/function will prevent complications associated with extended periods of bedrest.

II. Drugs/Biologics/Devices

1. Include the product, dose, route, and regimen.

200 IU of ISC(intranasal salmon calcitonin) daily for three months

2. Include the rationale for choosing the drug/biologic and dose, or for choosing the device to be used.

Intranasal salmon calcitonin (ISC) has been demonstrated to decrease pain and improve the level of activity in patients with acute vertebral osteoporotic compression fractures when administered within the first 5 days of onset of pain/injury. Recently, randomized

clinical trials have demonstrated calcitonin to be superior to NSAIDS in promoting early ambulation and preventing functional deterioration in patients with acute osteoporotic vertebral compression fractures.

2. Include the standard reference therapy against which the study product is being compared, or if the reference is a placebo. Include justification for inclusion of a placebo or non-treatment group. The study product is being compared to geriatric patients who are being treated nonoperatively and receive standard of care that does not include intranasal salmon calcitonin. Many geriatric patients with pelvic ring injuries who are treated nonoperatively. However, all patients will be prescribed calcium and vitamin D supplementation.

III. Recruitment Process

1. Describe the recruitment process; including how and where recruitment will take place. Recruitment will take place in the Emergency Room or at University of Missouri Main Hospital. Patients who have pelvic ring injuries will be screened for enrollment.
2. Describe any screening/baseline procedures. Patients will be screened by an attending orthopaedic traumatologist determining the type of pelvic ring injury based on x-rays and CT scans and decide upon operative treatment vs. nonoperative treatment. Patients who are deemed to benefit from nonoperative treatment will be screened for enrollment. Any patients who meet the criteria for age will then be further screened for inclusion and exclusion criteria as outlined below.

IV. Consent Process

1. Describe the consent process; including who will be approached for consent and what type of consent will be obtained from each subject population, if there is more than one. Study personnel will approach patient about research study in the emergency room or on the designated floor where they are admitted. Informed consent will be obtained at that time.

V. Inclusion/Exclusion Criteria

1. List the inclusion and exclusion criteria.
2. Inclusion:
 - Males or females over the age of 65 who sustain isolated pelvic ring injuries via a low-energy mechanism.

Exclusion:

- An open pelvic ring fracture
- Concomitant acetabular fracture
- They are on ISC prior to enrollment
- Use of medications for the treatment or prevention of Osteoporosis with the exemption of Vitamin D and Calcium supplementation
- Allergic or have contraindications to calcitonin or salmon

- Sustain other injuries in their spine (excluding transverse and spinous process fractures) or lower extremities
- Unwilling to participate in the study
- Nonambulatory at baseline
- Neurologic deficit associated with the pelvic ring injury

3. Describe restrictions on participation and appropriate screening procedures to ensure that the restrictions are maintained, including pregnancy testing.

- All patients meeting inclusion criteria will be screened by study personnel.

VI. Number of Subjects

1. Include anticipated enrollment number in this study. Include a break-down in numbers if there is more than one subject population.
 - 60 patients; 25 each group; 10 screen fails
2. Include statistical analysis or other justification for the number of subjects enrolled.

VII. Study Procedures/ Design/Treatment Plan

1. Include study procedures/design/plan; include the sequence and timing of study procedures (distinguish research procedures from those that are part of routine care). Include study duration and number of study visits required.
After obtaining informed consent, the following will be obtained:

Baseline: Treatment group will be prescribed 200IU of ISC daily for a period of 3 months. The control group will not be prescribed calcitonin. Participants will complete research only Iowa pelvis score questionnaire, SF-36 questionnaire and visual analogue scale (VAS) to assess subjective pain and function. Two-week follow up visit post discharge: participants will complete Iowa pelvis score questionnaire, SF-36 questionnaire and VAS to assess subjective pain and function. Participants will be referred for a standard of care DEXA bone density scan if they have no previous diagnosis of osteoporosis and no history of previous scan within a year. Six weeks post discharge: participants will complete Iowa pelvis score questionnaire, SF-36 questionnaire and VAS to assess subjective pain and function. Participants will undergo standard of care radiographic analysis of pelvic ring injury with AP/inlet and outlet pelvic x-rays 4. Twelve weeks post discharge: Participants will complete Iowa pelvis score questionnaire, SF-36 questionnaire and VAS to assess subjective pain and function. Participants will undergo standard of care radiographic analysis of pelvic ring injury with AP/inlet and outlet pelvic x-rays - Participants will perform a timed up and go (TUG) test.

2. Blinding, including justification for blinding or not blinding the trial. Describe un-blinding procedures.

After informed consent is obtained, all patients who meet eligibility criteria will be randomized into one of two groups. Randomization will be achieved by numbering 50 sealed white envelopes (25 control, 25 treatment). There is no blinding to the randomization. It would be difficult to blind the participants, or the research personnel. We do not believe there will be any significant bias that can be corrected with blinding.

Treatment: 200IUof ISC daily for a period of 3 month

Control: Will not be prescribed calcitonin (ISC)

3. Justification of why participants will not receive routine care or will have current therapy stopped.
Patients will receive routine care during this study.
4. Definition of treatment failure or participant removal criteria.
Patients will be removed if they do not return to their follow-up visits or do not complete the study specific tasks.
5. Description of what happens to participants receiving therapy when study ends or if participation in the study ends prematurely.
Routine care will continue per the physician's standard of care treatment.
6. Include sub-studies or banking information (correlative/special studies)
None

VIII. Potential Risks/Adverse Events

1. Describe reasonably foreseeable risks or discomforts to the subjects and steps to minimize risks. This study is expected to have minimal risk to the patient since we are using the FDA approved dosage for this study. This risk will be minimized by going over the purpose of the study with the patient before obtaining consent, and allowing withdrawal from the study at any time.
2. Describe any stopping rules. Stopping rules would include any reactions or side effects to ISC or per the provider's discretion.
3. Include the plan for reporting unanticipated problems or deviations. This plan must include a five-day reporting requirement to the IRB once becoming aware of an event.

IX. Anticipated Benefits

1. Include both direct and indirect benefits for either the individual or society.
The benefit to society is to provide data that will eventually lead to decrease pain in patients with pelvic ring fractures by using intranasal Calcitonin within 5 days of injury.

No direct benefits will be promised. Subjects can expect to help add to public knowledge about the effect of pelvic rings fractures in elderly patients.

X. Compensation

1. Describe the amount, method, and timing of disbursement. Compensation can include checks, cash, gifts, extra/course credit, etc.

Subjects will be paid \$10 for each visit they complete but will only receive one check once they finish their 12 week visit. Subjects will be paid \$30 at their final visit.

XI. Costs

1. Detail costs of study procedures, drugs, biologics, or devices and identify who will cover the cost. All costs are being covered by the AOTNA grant. No additional costs to the participants for being enrolled in the study. Participants will pay for all standard of care costs.

Cost:

\$1,800 – Calcitonin Costs (\$72 per participant x 25 participants)

\$1,500 – Participant Stipend (\$30 per participant x 50 participants)

\$6,500 – Study Coordinator (0.7 calendar months, 5.9% effort, of assistance, covering salary and benefits for this effort)

Total: \$9,800

XII. Data Safety Monitoring Plan

Describe the plan to monitor the data, if necessary. A plan is required for treatment and/or intervention studies, sensitive data are being collected, there is a possibility for subjects to experience adverse events, etc. Adverse events will be reported to the IRB as necessary within 5 days of becoming aware of the event.

1. The plan should include when something needs to be reported
2. The frequency of the monitoring, such as points in time or after a specific number of participants are enrolled
3. Who will conduct the monitoring, such as a data board, medical monitor, investigator, independent physician; the specific data to be monitored
4. Procedures for analysis and interpretation of the data
5. Actions to be taken upon specific events or end points
6. Procedures for communication from the data monitor to this site.

XIV. References/Appendices

1. Include findings from a literature search or pilot study must be outlined including appropriate detailed references to earlier studies and data.

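### The removal rule makes no exception for patients physically unable to do the week-12 timed up and go, so a poor functional outcome can decide who enters the only performance-based comparison

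*Protocol*

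**What the plan says.** Protocol section VII.1 lists the TUG among the twelve-week procedures and at no other visit: "Participants will perform a timed up and go (TUG) test". It defines no result for a patient who attends but cannot do the test.

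Section VII.4, on treatment failure and removal, reads: "Patients will be removed if they do not return to their follow-up visits or do not complete the study specific tasks". It does not except physical inability, and it does not say whether removal means ending participation or also leaving the patient out of the analysis.

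Three other statements bear on the point:

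- Section I.2 anticipates that treated patients "will demonstrate decreased pain scores and improved subjective and objective function". The secondary objective in section I.1 is "To compare function and activity over a three-month period in geriatric patients with pelvic ring injuries".
- For the questionnaires, section VII.1 says "participants will complete Iowa pelvis score questionnaire, SF-36 questionnaire and VAS to assess subjective pain and function". The x-rays concern healing. The TUG is therefore the only performance-based measure of function.
- Section V excludes patients who are "Nonambulatory at baseline".

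**The concern.** Inability to stand and walk at week 12 is the worst result a TUG can give. Patients who could not walk at baseline are excluded, so this inability would have arisen after enrolment. It is part of the outcome under comparison.

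Applied literally, section VII.4 turns that outcome into a reason for removal. If calcitonin restores walking, part of its benefit is that fewer treated patients are unable to do the test. Dropping those who are unable discards that part. It takes more of the worst patients out of the control arm than out of the calcitonin arm, and the remaining difference shrinks toward zero.

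The other function measures are self-reported, and the trial is open ("There is no blinding to the randomization"), so the objective measure is worth protecting.

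**Working it through.** **Reading the two rules together.** VII.1 makes the TUG a week-12 study task. VII.4 removes patients who do not complete study tasks. Nothing in either section exempts a patient who tries and cannot. A non-performer therefore meets the removal wording.

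**Inputs from the protocol.** 25 patients per arm (section VI: "60 patients; 25 each group; 10 screen fails"), one TUG, open label. The protocol gives no TUG distribution, effect size, power or proportion unable, so there is no planned figure to reproduce.

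**Assumed inputs (not in the protocol).** Log TUG time is normal, with control median 20 s, SD 0.5 and a true shift of 0.30 in favour of calcitonin. Patients slower than a cut-off T are unable to do the test. The cut-off is varied because nothing in the protocol fixes it.

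**Proportion unable.** Let c = ln(T/20)/0.5 and d = 0.30/0.5 = 0.6. Then the proportion unable is 1 − Φ(c) among controls and 1 − Φ(c + d) under calcitonin. For T = 30 s, c = 0.405/0.5 = 0.811, which gives 21% of controls. For calcitonin, 1 − Φ(1.411) = 8%. That is about 5 of 25 against 2 of 25.

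**Difference among performers.** From the truncated normal, the difference is 0.5 × [d + φ(c+d)/Φ(c+d) − φ(c)/Φ(c)]. For T = 30 s this is 0.5 × (0.6 + 0.160 − 0.363) = 0.199, so about one third of the true 0.30 is lost.

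**Power** was simulated at 25 per arm, two-sided 5%. A t-test on log time with non-performers dropped was set against a Mann-Whitney test with non-performers tied at the worst rank. Repeat runs agreed to within about two percentage points.

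| Cut-off | Controls unable | Difference among performers (true 0.30) | Power, dropped | Power, ranked worst |
|---|---|---|---|---|
| 30 s | 21% | 0.20 | 35% | 52% |
| 40 s | 8% | 0.24 | 46% | 53% |
| 45 s | 5% | 0.26 | 49% | 52% |
| 60 s | about 1% | 0.29 | 52% | 51% |

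Using Mann-Whitney for performers as well gives 32% at 30 s, so the loss comes from exclusion and not from the choice of test. With no true effect, both approaches reject about 5% of the time.

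**Second model.** With a standardized effect of 0.5 or 0.8 SD on a normal mobility scale and 20% of controls unable, the difference among performers is 0.33 or 0.56 SD (66% or 70% of the truth). Power, by Mann-Whitney throughout, is 24% against 39%, or 55% against 76%. The direction is the same.

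**The case against.** The strongest case against the point has four parts.

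*Scoring belongs in a SAP.* How to score inability, and which test to use, is commonly left to a SAP, and this trial's SAP is not shown. That stands. A reader might infer that a patient unable to do the TUG gets no value, or that a completers-only analysis is planned. The protocol says neither, and a SAP could assign a worst rank. What remains is the removal rule, which the protocol does state. A SAP that ranks these patients worst would have to be reconciled with a rule that removes them.

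*'Removed' is undefined.* It may mean only that participation ends. The TUG falls at the last scheduled visit, so no later visit would be lost. An attempt recorded as a failure might also count as completing the task. Both readings are open, and the text settles neither. A reader might go further and infer that the patient's pain and questionnaire data are deleted too; the protocol does not say so.

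*The size depends on the cut-off.* This stands. The loss is large only if about a fifth of controls are unable, in a trial that excludes patients who cannot walk at baseline. It is small at 5% and gone at about 1%. Where inability has nothing to do with treatment or walking time, ranking it worst costs power: with 10% unable per arm, 35% against 51% for performers only.

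*The consequence is limited.* Pain is the primary objective. The Iowa score and SF-36 are collected at all four assessments and can be completed by someone who cannot stand, so the function objective does not rest on the TUG alone. This also stands.

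**Conclusion.** The point holds as a defect in stated text. Sections VII.1 and VII.4 together allow a poor functional outcome after randomization to decide who is in the only performance-based comparison. If calcitonin helps walking, the bias is toward no difference.

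Its size is unknown. Under the assumed log-normal model with a shift of 0.30, the loss of power is about 17 percentage points (52 − 35) if 21% of controls are unable, 7 points (53 − 46) at 8%, 3 points (52 − 49) at 5%, and none at about 1%. All of these proportions, the shift and the sharp cut-off are assumptions.

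The effect is on one measure of a secondary objective. The change is worth making because it costs little and because inability not recorded at the visit may not be distinguishable later from refusal.

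**What to change.** State in sections VII.1 and VII.4: *Inability to perform the TUG at week 12 because of pain or mobility is recorded as the result 'unable', with the reason, and is not a ground for removal.* Keep these patients in the TUG comparison as the worst outcome, for example at the worst rank, and report the number unable per arm. The exact test can be set in the SAP. Section VII.4 should also say what removal means for data already collected.

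The cost is a short text change and one tick box on the visit form. There are two small downsides. The result becomes a rank comparison and not a mean difference in seconds. The reason for inability is also judged by unblinded staff, so all non-performance should be reported by arm, whatever the reason given.

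### The timed up and go test, the only performance-based function measure, is scheduled only at week 12, so the trial can compare objective function at three months but not its course or an early mobility benefit

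*Protocol*

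**What the plan says.** The secondary objective in section I.1 is "To compare function and activity over a three-month period in geriatric patients with pelvic ring injuries who are treated nonoperatively", with and without intranasal calcitonin. Section I.2 expects that treated patients "will demonstrate decreased pain scores and improved subjective and objective function". Section II.2 supports the choice of drug with trials in vertebral fracture in which calcitonin was "superior to NSAIDS in promoting early ambulation and preventing functional deterioration".

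Section VII.1 sets four assessment times. At baseline, "Participants will complete research only Iowa pelvis score questionnaire, SF-36 questionnaire and visual analogue scale (VAS) to assess subjective pain and function". The same three instruments recur at two weeks ("Two-week follow up visit post discharge: participants will complete Iowa pelvis score questionnaire, SF-36 questionnaire and VAS to assess subjective pain and function"), six weeks and twelve weeks after discharge. TUG appears only after the twelve-week items: "Participants will perform a timed up and go (TUG) test". The protocol does not mention it anywhere else.

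Section VII.2 states that the trial is not blinded. Section VII.4 removes patients who miss follow-up visits or who "do not complete the study specific tasks".

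**The concern.** The protocol's argument for the drug is about early effects: walking sooner, and avoiding the complications of prolonged bedrest. The one measure that records what a patient can physically do is taken at the last visit, when many patients in either arm may already have recovered. If calcitonin speeds up mobilisation without changing where patients end up, TUG at week 12 will show no difference. That early benefit could then appear only in questionnaires completed by patients who know their treatment.

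An analysis plan cannot repair this, because week 2 and week 6 values that were never collected cannot be recovered.

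A second, conditional problem concerns the removal rule. If TUG counts as a study-specific task, a patient too disabled to complete it meets the rule as written. Those patients have the worst result on this measure. If their number differs between arms, leaving them out distorts the week-12 comparison.

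**Working it through.** **Schedule, counted visit by visit (section VII.1).**

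| Time point | Self-reported function (Iowa, SF-36) | Performance test (TUG) |
|---|---|---|
| Baseline | yes | no |
| Week 2 | yes | no |
| Week 6 | yes | no |
| Week 12 | yes | yes |
| Total | 4 of 4 | 1 of 4 |

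The x-rays at weeks 6 and 12 serve the exploratory objective on radiographic healing and do not measure function. One time point supports a between-arm difference at that time. It supports no change, slope or course.

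**What each passage asks for.** The three-month span comes from the secondary objective in I.1, which speaks of function and activity without the word objective. Objective function comes from the expectation in I.2, which gives no time course. Early ambulation comes from II.2. The schedule meets I.1 through the questionnaires and I.2 through TUG at week 12. It provides no objective measure of what II.2 emphasises.

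**Illustrative power.** The protocol gives no alpha, power, standard deviation (SD) or effect size for TUG, so there is no figure of its own to reproduce. The only input from the protocol is 25 patients per arm (VI.1, VII.2). Assumed: two-sided alpha 5%, power 80%, correlation between visits (rho) 0.5 to 0.7, equal variance at each visit, and every patient able to do the test.

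- Single TUG at week 12: the normal approximation gives (1.960 + 0.842) × sqrt(2/25) = 0.79 SD. The two-sample t-test gives a detectable difference of 0.809 SD.
- Mean of weeks 2, 6 and 12: its variance relative to one visit is (1 + 2 × rho)/3, which is 0.667 at rho 0.5 and 0.80 at rho 0.7. The SD factors are sqrt(0.667) = 0.816 and sqrt(0.80) = 0.894.
- Detectable difference for that mean: 0.809 × 0.816 = 0.660 SD, or 0.809 × 0.894 = 0.723 SD.
- Power for an assumed constant effect of 0.6 SD: 54.7% with the single visit. With the three-visit mean it is 72.1% (rho 0.5) or 64.2% (rho 0.7).

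**What these figures leave out.** They assume the same effect at all three visits. The three-visit mean is more sensitive than week 12 alone only if the average effect exceeds 0.816 (rho 0.5) or 0.894 (rho 0.7) of the week-12 effect. If the effect grows with time, averaging can lose power. If it has vanished by week 12, the single TUG has only its 5% false-positive rate. The figures also do not describe a rank-based analysis with many tied worst values.

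**The case against.** The strongest reply is that nothing is contradicted. No sentence promises objective function over three months: that reading joins the time span in I.1 to the word objective in I.2. Function over three months is covered by the Iowa score and SF-36 at all four time points. This stands, and it rules out the stronger claim a reader might infer, that the trial cannot compare objective function or fails its secondary objective.

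A reader might also take the missing baseline TUG as a flaw that invalidates the week-12 comparison. It does not. Under 1:1 randomisation the arms can be compared at week 12 without a baseline value, which would add precision only. A baseline TUG shortly after a pelvic fracture may also not be feasible.

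TUG is not protected from the lack of blinding either. It depends on the patient's effort and is performed in a trial where participants and research personnel know the allocation. Its advantage over the questionnaires is one of degree.

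On VII.4, the protocol does not define the study-specific tasks, does not mention inability to do TUG, and does not say that data already collected are discarded. How such patients are analysed may be settled in an analysis plan that is not shown. It is therefore not established that they will be lost. What remains is that the rule as written makes no exception for inability.

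Finally, the power gain assumes a constant effect, whereas the main worry is an effect that fades. That is correct, so the power figures do not carry the argument. The gap in the schedule remains.

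**Conclusion.** The point holds in limited form. The trial can make a valid between-arm comparison of TUG at three months, provided patients are retained. It cannot describe the course of objective function or detect an early mobility benefit that does not last to week 12, although early ambulation is central to the rationale. The repeated measures fill the gap only with self-report from unblinded patients.

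The size is one objective measurement out of four possible time points. The gain in detectable difference, from 0.81 SD to between 0.66 and 0.72 SD, is an illustration that rests on a constant effect, equal variances, rho of 0.5 to 0.7 and nobody unable to do the test.

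The removal problem is conditional on reading VII.4 literally and counting TUG among the study-specific tasks.

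The change should be made, but it is not critical. TUG belongs to a secondary objective, and pain, the primary objective, is measured at all four time points.

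**What to change.** In VII.1, add TUG at the two-week and six-week visits for patients able to attempt it, with baseline optional. Record inability to perform the test as a result and rank it worst. State in VII.4 that inability to do TUG is not a reason for removal. Compare the arms at each visit with a rank-based analysis, so that patients who cannot do the test stay in the comparison.

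If early testing is judged impractical, restate the objective-function comparison as a week-12 comparison only, and keep the exemption in VII.4.

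The cost is a protocol amendment and a few minutes at two visits that already take place, using a test already planned for week 12. The time per test is an estimate, and the budget in section XI allows only 0.7 calendar months of coordinator time. The statistical drawback is that many patients may share the worst rank at week 2, which would weaken that visit's comparison.

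### The stated allocation method, numbering 50 sealed white envelopes, names no random order, opacity, opening sequence or custodian, leaving room for selection bias at entry to an open-label trial

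*Protocol*

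**What the plan says.** Allocation is described in one place, Protocol section VII, item 2 (Blinding). It first gives the timing: "After informed consent is obtained, all patients who meet eligibility criteria will be randomized into one of two groups". It then gives the method: "Randomization will be achieved by numbering 50 sealed white envelopes (25 control, 25 treatment". Next come three remarks on blinding: "There is no blinding to the randomization", then "It would be difficult to blind the participants, or the research personnel", then "We do not believe there will be any significant bias that can be corrected with blinding".

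Three other places bear on the point:

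- Section VI, item 1 gives the numbers: "60 patients; 25 each group; 10 screen fails".
- Section IV, item 1 says who recruits: "Study personnel will approach patient about research study in the emergency room or on the designated floor where they are admitted".
- Section VII, item 1 lists the VAS, SF-36 and Iowa pelvis score at baseline and at each follow-up visit, as measures of subjective pain and function.

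**The concern.** A randomised comparison needs two things before any patient is assigned: an order of arms produced by chance, and a way of keeping the next arm unknown to whoever decides on the patient's entry. The protocol chose to describe its method and described a labelling step instead.

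Concealing the next assignment differs from blinding the treatment, and it remains feasible when blinding is not. In an open-label trial it is the main safeguard left at entry. If recruiting staff can learn or choose the next arm, they may, without intending to, change when or how they approach a patient. The arms could then differ in pain, injury severity or motivation before treatment begins. Section I, item 2 already expects the calcitonin group to do better, the outcomes are subjective, and there are only 25 patients per arm, so a few steered entries could matter.

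This is not something to leave to an analysis plan. How envelopes are prepared and held is a rule of conduct that must be in force before the first patient.

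**Working it through.** **1. Counts.** Section VII, item 2: 25 + 25 = 50 envelopes. Section VI, item 1: 25 + 25 + 10 screen failures = 60. The figures agree, so the numbers are not at fault.

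**2. What concealed random allocation needs, against what the text gives.**

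| Element | Protocol text |
|---|---|
| Random source for the order of arms | None named; the envelopes are numbered |
| Contents cannot be read from outside | Sealed and white; opacity not stated |
| Opened strictly in sequence | Not stated; numbering suggests it |
| Patient tied to an envelope before it is opened | Not stated |
| Prepared and held by someone outside recruitment | Not stated |
| Assignment after consent and eligibility | Stated |
| Assignment after baseline questionnaires | Not stated; section VII, item 1 mentions the prescription before the questionnaires |
| Log kept | Not stated |

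No other section fills these gaps.

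**3. What literal compliance would allow.** Suppose the 50 envelopes were filled in strict alternation. This is an assumption; the text neither says it nor rules it out. Once the first arm and the pattern were known, the other 50 − 1 = 49 assignments would be known too. A well-shuffled, opaque set opened in order would satisfy the same sentence. The wording does not separate the two, and that is the defect.

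**4. Whether the remedy should use small blocks.** Staff in an open-label trial can tally past assignments and guess the arm used less so far. For a randomly ordered set with n per arm, the expected number of correct guesses is

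n + 4^n / (2 × C(2n, n)) − 1/2.

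- One set of 25/25 (n = 25): 25 + 2^49 / C(50, 25) − 0.5 = 28.95 of 50, against 25 by chance. An exact recursion gives the same 28.95.
- Block of 4 (n = 2): 2 + 16 / (2 × 6) − 0.5 = 2.83 of 4, which is 2.83 / 4 × 50 = 35.4 of 50.
- Block of 6 (n = 3): 3 + 64 / (2 × 20) − 0.5 = 4.10 of 6, which is 4.10 / 6 × 50 = 34.2 of 50.
- Equal numbers of blocks of 4 and 6: (2.83 + 4.10) / 10 × 50 = 34.7 of 50. This guess does not require knowing the block sizes.

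Small blocks would make assignments easier to guess than one permutation of 25 and 25. These figures guide the choice of remedy. They do not measure the defect, because 28.95 applies to any properly shuffled and concealed 25/25 list in an open-label trial.

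**The case against.** The strongest reply is that the paragraph already carries the intent. It says patients are randomised, and only after consent. Sealing an envelope has little purpose except concealment, and numbering most naturally implies use in order. On this view the point is a request for detail. Part of that stands: these words give partial protection, and the fair claim is that the text does not exclude a foreseeable or chosen assignment. They still supply no random source, opacity or custodian.

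Several stronger readings are tempting and are not supported:

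- **That "There is no blinding to the randomization" admits the next assignment is disclosed.** It stands under the blinding heading and is followed at once by the difficulty of blinding participants and personnel. In context it means open-label treatment. It is loosely worded and worth rewording, but it is not evidence that concealment is absent. Equally, the protocol's view that blinding would correct no significant bias concerns blinding only and does not answer this point.
- **That the people who obtain consent also open the envelopes.** Study personnel approach and screen patients, and an attending traumatologist screens first (section III, item 2). Who opens envelopes is not stated. The gap is that no separation is required.
- **That the fixed pool of 25 and 25 is itself a fault because staff can count down.** With a shuffled list, on average only the last 2 × 25/26 = 1.92 assignments are certain, and the usual alternative of small blocks is more predictable. The fixed total also matches sections VI and XI, which plan for and cost 25 treated participants.
- **That no analysis could help.** Baseline scores are collected, so measured imbalance could be adjusted for if they are recorded before assignment is known. Unmeasured imbalance could not.

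**Conclusion.** The point holds as a shortcoming in the stated method, and it should be corrected. Followed to the letter, section VII, item 2 would permit an order that is systematic, readable or chosen, in an open-label trial whose main outcomes are subjective.

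Its effect on the treatment comparison cannot be sized from the protocol. That would depend on how the envelopes are actually filled and held, and on how staff respond. A reader might infer that allocation will be subverted, or that the comparison is already invalid; the protocol shows neither. With a true shuffle, opaque envelopes and sequential opening, the defect would be one of wording only.

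The conclusion assumes that no separate randomisation procedure supplies the missing elements. The protocol refers to none.

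**What to change.** In section VII, item 2, keep the 25/25 total and replace the sentence on envelopes with:

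> The order of 25 treatment and 25 control assignments is generated by computer as one random permutation, without small blocks, by a colleague not involved in recruitment, who places it in sequentially numbered, opaque, tamper-evident sealed envelopes. After consent, confirmed eligibility and completion of the baseline questionnaires, study personnel write the patient ID, date and time on the next envelope in sequence before opening it. A log and the opened envelopes are kept.

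Reword the sentence on blinding to the randomization as:

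> Treatment is open-label; the allocation sequence is concealed until assignment.

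The cost is one paragraph, about an hour of an uninvolved colleague's time, and the upkeep of a log. The sample size and the 25/25 split do not change. Some predictability from tallying remains, as in any open-label trial with a fixed split.
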